# 7. Statistical Methods

## 7.1 General Principles

All data processing, summarization and analyses will be performed using Labcorp Drug Development's SAS® Environment / Version 9.4 (or later) of the SAS® statistical software package.

The following principles will be applied to all tables, figures and listings (TFLs) unless otherwise stated:

Sponsor Name: Pharma Mar S.A. Sponsor Protocol ID: APL-D-003-20

Labcorp Drug Development Study ID: 000000213894

Principle	Value
Significant tests	All significance tests will be 2-sided and use a 0.05
	a-level unless specified otherwise, eg primary and key
	secondary efficacy endpoint analysis explained below.
Treatment group labels and	Plitidepsin 2.5mg
order presented	Plitidepsin 1.5mg
	Control Arm
Tables	Data in summary tables presented by treatment group,
	assessment/parameter (where applicable) and visit
	(where applicable).
Listings	All data collected presented by treatment group,
	country, site, patient, assessment/parameter (where
	applicable) and visit (where applicable), unless
	otherwise specified.
Descriptive summary	Number of patients/observations with non-missing data
statistics for continuous	(n), mean, standard deviation (SD), median,
variables	Interquartile range (25" and 75" percentiles), range
	(minimum and maximum). If n=0 then other statistics
Descriptive summany	Will De Didlik.
descriptive summary	ar difference in percentages presented to 1 desimal
Denominator for	Number of patients per treatment group in the analysis
percentages	nonulation unless stated otherwise in table shell(s)
Include "Missing" as	Yes when the number missing is greater than zero for
category	at least one treatment group.
Display for 0 percentages	Leave <blank></blank>
Display to one more decimal	Mean
place than collected value	Mean Difference
F	Median
	25 th and 75 th percentiles
	Confidence Interval (CI)
Display to two more decimal	SD
places than collected value	Standard Error (SE)
Display for p-values	x.xxxx for p-value $\geq 0.0001$
	< 0.0001 for p-value < 0.0001
Display for hazard and odds	3 decimal places
ratio and the corresponding	
95% CI	
Date Format	DDMMMYYYY
Display for analysis not done	NC (not calculated), NA (not applicable), ND (not done),
	or NR (not reached). Refer to table shells.

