# 7.6.2.2 Secondary Efficacy Endpoints

Descriptive statistics for the secondary efficacy endpoints will be presented by treatment group and by study visit where appropriate.

Clinical status by the 11 category WHO Clinical Progression Scale, at Day 8 (±1).

The clinical status, as assessed on the 11-point WHO Clinical Progression Scale on Day 8 will be summarised by treatment group. The percentage of patients within each category will be presented and the 95% CI will be computed using the Goodman method for the multinomial proportions.

In case of missing clinical status on Day 8, the following approach will be used:

- If patient dies before or on Day 8  $\rightarrow$  clinical status = 10.
- Otherwise, the last observation carried forward (LOCF) approach will be used, where the last recorded clinical status for the same patient is carried forward to the missing clinical status on Day 8.

The clinical status on Day 8 between each dose of plitidepsin versus control arm will be compared using a proportional odds model. The model will be adjusted for the randomisation stratification factors. The odds ratios, 95% CIs, and 2-sided p-values for the comparison of each dose of plitidepsin versus control arm will be presented.

• Total duration of advanced oxygen support (high-flow nasal oxygen, ECMO, non-invasive ventilation or mechanical ventilation).

The total duration of advanced oxygen support (in days), defined as the number of days with any type of advanced oxygen support (eg, high-flow nasal oxygen, non-invasive mechanical ventilation, invasive mechanical ventilation or ECMO)

Duration of advanced oxygen support (days) = (date of last advanced oxygen support required – date of randomisation) + 1 – off-advanced oxygen support days

If last advanced oxygen support date is missing then date of death or the last visit or the last telephone contact with the patient, whichever occurs later, will be used.

The number and percentage of patients who required an advanced oxygen support together with total duration of advanced oxygen support (in days) will be summarised by treatment group. Only patients who required an advanced oxygen support will be included in the summary of the total duration of advanced oxygen support.

• *Percentage of patients in each study group requiring admission to ICU on Days 4, 8, 15, and 31.* 

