# 7.6.2.3 Other Secondary Efficacy Endpoints

Descriptive statistics for the other secondary efficacy endpoints will be presented by treatment group and by study visit where appropriate.

For time-to-event endpoints, similar methods will be used as specified for the analyses of the primary variable. For binary endpoints, the treatment group comparisons will be performed at Day 8 only, with descriptive statistics provided for each clinic visit.

• Percentage of patients in each study group who require hospital re-admission related to COVID-19 through Day 31.

The percentage of patients who require re-admission for COVID-19 related signs or symptoms through Day 31 will be presented by treatment group and Clopper–Pearson 95% CI will be computed for the binomial proportion.

Only patients who discharged from the hospital will be included in the analysis of the re-admission for COVID-19 related signs or symptoms.

• Percentage of patients in each study group and in each of the categories of the 11-point WHO Clinical Progression Scale on Days 4, 8, 15, and 31.

The clinical status, as assessed on the 11-point WHO Clinical Progression Scale will be summarised on Days 4, 8, 15, and 31, by treatment group.

In case of missing clinical status at the time point, the following approach will be used:

- If patient dies before or on the time point → clinical status = 10.
- Otherwise, LOCF approach will be used, where the last recorded clinical status for the same patient is carried forward to the missing clinical status at the time point.
- Percentage of patients in each study group requiring oxygen therapy on Days 4, 8, 15, and 31.

The percentage of patients who require oxygen therapy on Days 4, 8, 15, and 31, will be presented by treatment group. Clopper–Pearson 95% CI will be computed for the binomial proportions.

If a patient requires any change in the oxygen therapy on Day 4, 8, 15, or 31, the new oxygen status will be selected, e.g. if a patient changes from "Low-flow" to "No supplemental oxygen needed" on Day 4, "Require oxygen therapy on Day 4'' = No. On the other hand, if a patient changes from "No supplemental oxygen needed" to "Low-flow" on Day 8, "Require oxygen therapy on Day 8" = Yes.

The difference in the percentage of patients who require oxygen therapy on Days 4, 8, 15, and 31 between each dose of plitidepsin versus control arm

will be presented for each dose of plitidepsin and the exact 95% CI will be computed for the difference in the percentage.

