#### CONFIDENTIAL

\*Body weight and height should be measured at screening.

- 1 Informed consent: Must be obtained before the patient undergoes any study-specific procedure
- 2 Selection criteria: Confirm that patient meets all inclusion criteria and none of the exclusion criteria
- 3 Vital signs: Temperature, sitting blood pressure, heart rate, respiratory rate, PaO2 (obtained either by arterial blood gas analyses or from saturation of oxygen (SpO2) by pulse oximetry, and its respective FiO2 to be measured at screening, on Days 1 to 3 just before start and end of each plitidepsin infusion (plitidepsin groups)/once daily on Days 1 to 3 (control group), further once daily while the patient is hospitalised, and on Days 8, and 31 (±3 days). To estimate the PaO2/FiO2 ratio, the required equation would be used for imputing PaO2 from SpO2, and the information on the oxygen delivery devices and oxygen flow prescribed would be utilised for imputation of FiO2.
- 4 ECG: QTcF prolongation to be assessed at screening and on Days 1, 3 (postinfusion), and 31 (±3 days), and any QTcF values >500 msec will be flagged as increasing the likelihood of the treatment being proarrhythmic (per ICH Guidance E14)
- 5 Haematology: RBC, haemoglobin, haematocrit, WBC with differential, platelet count. Testing to be performed by the local laboratory for screening and by central laboratory for on-study tests (tests performed within 24 hours of screening do not have to be repeated)

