## 2.11.2 Summary Statistics Displays for categorical variables

For categorical variables, the number (n) and percentage (%) of patients with non-missing data per category will be the default summary presentation, and where appropriate and present, the number of missing values as a "Missing" category.

Categorical variables will be presented as follows:

Statistics	Presentation/Rounding rule			
number of patients with valid	whole number; if n is 0 for categorical data, then n (%) statistic will			
observations [n]	be displayed as 0			
number of patients [N]	whole number			
percentage of patients with valid observations [%]	Percentage values are to be rounded and presented to one decimal place, for example, 52.3. If the calculated percentage is > 0.0 but < 0.1 then < 0.1 is to be presented in the relevant table and/or listing. If the calculated percentage is 100 then present 100.0 in the relevant table and/or listing (i.e., to 1 decimal place) as this will ensure correct alignment.			

Percentages will be presented without % sign. Percentages will be displayed with one space between "n" and "(", e.g., 76 (16.5). No percentages will be presented for cases with 0 counts:

For any expected data in tables (e.g., demography, disposition), if the total number of patients in one category (e.g., Sex, Race or Age group etc.) is not equal to N, then a Missing category will be added. "Missing" cases will be included in the denominator. Where "Missing" cases are excluded from the denominator, details are provided on the relevant footnotes within the table.

Missing category will not be displayed if there are all 0's in a row.

	Placebo
	(N=20)
	n (%)
ace	
White	2 (10.0)
Black	0
Asian	8 ( 40.0)
Other	5 ( 25.0)
Missing	5 ( 25.0)

For by-visit tables with categorical endpoints, patients who provide a missing / non-evaluable response but are still ongoing in the trial and attend the visit should be included in a Missing category.

Summary statistics for categorical variables will be aligned according to place values, i.e., line up units under units, tens under tens, etc.

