## Table 14.2.3.6.1 Patients who Require Oxygen Therapy (Full Analysis Set)

Timepoint Variable	Plitidepsin 2.5mg (N=XXX)	Plitidepsin 1.5mg (N=XXX)	Control Arm (N=XXX)
Day 4			
Patients at Day 4, n1	XXX	XXX	XXX
Require Oxygen Therapy, n (%)	xx (xx.x)	xx (xx.x)	xx (xx.x)
95% CI for Require Oxygen Therapy (%) [a]	XX.X - XX.X	XX.X - XX.X	XX.X - XX.X
Non Require Oxygen Therapy, n (%)	xx (xx.x)	xx (xx.x)	xx (xx.x)
Difference of Oxygen Therapy Rate (%) [b]	XX.X	XX.X	
95% CI for Difference of Oxygen Therapy Rate (%) [c]	XX.X - XX.X	XX.X - XX.X	
Day 8			
Patients at Day 8, n1	XXX	XXX	XXX
Require Oxygen Therapy, n (%)	xx (xx.x)	xx (xx.x)	xx (xx.x)
95% CI for Require Oxygen Therapy (%) [a]	XX.X - XX.X	XX.X - XX.X	XX.X - XX.X
Non Require Oxygen Therapy, n (%)	xx (xx.x)	xx (xx.x)	xx (xx.x)
Difference of Oxygen Therapy Rate (%) [b]	XX.X	XX.X	
95% CI for Difference of Oxygen Therapy Rate (%) [c]	XX.X - XX.X	XX.X - XX.X	
Adjusted Odds Ratio [d,e]	X.XXX	X.XXX	
95% CI for Adjusted Odds Ratio [d,e]	x.xxx - x.xxx	X.XXX - X.XXX	
2-sided p-value [d]	x.xxx	X.XXX	
Day 15			
Patients at Day 15, n1	XXX	XXX	XXX
Require Oxygen Therapy, n (%)	xx (xx.x)	xx (xx.x)	xx (xx.x)
95% CI for Require Oxygen Therapy (%) [a]	XX.X - XX.X	XX.X - XX.X	XX.X - XX.X
Non Require Oxygen Therapy, n (%)	xx (xx.x)	xx (xx.x)	xx (xx.x)
Difference of Oxygen Therapy Rate (%) [b]	XX.X	XX.X	
95% CI for Difference of Oxygen Therapy Rate (%) [c]	XX.X - XX.X	XX.X - XX.X	

Day 31			
Patients at Day 31, n1	XXX	XXX	XXX
Require Oxygen Therapy, n (%)	xx (xx.x)	xx (xx.x)	xx (xx.x)
95% CI for Require Oxygen Therapy (%) [a]	XX.X - XX.X	XX.X - XX.X	XX.X - XX.X
Non Require Oxygen Therapy, n (%)	xx (xx.x)	xx (xx.x)	xx (xx.x)
Difference of Oxygen Therapy Rate (%) [b]	XX.X	XX.X	
95% CI for Difference of Oxygen Therapy Rate (%) [c]	xx.x - xx.x	XX.X - XX.X	

N = number of patients in analysis set; n = number of patients in each category; n1 = number of patients with data available at timepoint; % = percentages are calculated based on n1 as the denominator; CI = Confidence interval.

[a] Clopper-Pearson 95% confidence interval.

[b] Difference of Oxygen Therapy Rate = Oxygen Therapy Rate for the plitidepsin arm - Oxygen Therapy Rate for control arm.

[c] Exact 95% confidence interval.

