N = number of patients in analysis set; n = number of patients in each category; n1 = number of patients with data available at timepoint; % = percentages are calculated based on n1 as the denominator; CI = Confidence interval; ECMO = extracorporeal membrane oxygenation.

[a] Clopper-Pearson 95% confidence interval.

[b] Difference of Invasive Mechanical Ventilation or ECMO Rate = Invasive Mechanical Ventilation or ECMO Rate for the plitidepsin arm - Invasive Mechanical Ventilation or ECMO for control arm.

[c] Exact 95% confidence interval.

[d] Adjusted Odds Ratio, 95% CI and 2-sided p-values based on a stratified logistic regression model with fixed effects of treatment group and randomisation stratification factors, ie, geographical region (Europe vs. Rest of the World), Charlson Comorbidity Index (0-1 vs. >1) and pre-baseline Barthel index (≥90 versus <90) as derived using the eCRF data as covariates. [e] Statistics calculated relative to Control Arm.

Reference: Listing 16.2.6.4

Programming notes (not part of the table):

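### The on-the-day oxygen and ventilation rates drop patients who have already died, so the arms are compared among survivors, including in the Day 8 test

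*SAP*

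**What the plan says.** SAP Section 7.6.2.3 plans the percentage of patients on oxygen therapy on Days 4, 8, 15 and 31, with differences from control. On Day 8 it adds a stratified logistic regression with an odds ratio and p-value. High-flow oxygen, non-invasive ventilation and invasive ventilation/ECMO follow the same method.

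The shells divide by n1. Table 14.2.3.6.1 states "n1 = number of patients with data available at timepoint; % = percentages are calculated based on n1 as the denominator", and in Table 14.2.3.11.1 too "percentages are calculated based on n1 as the denominator". Section 7.1 would otherwise use the arm's analysis population. Section 2.11.2 of the shells normally keeps missing cases in the denominator; where they "are excluded from the denominator, details are provided on the relevant footnotes within the table".

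The only rule for deriving the status on a given day covers a change on that day, when "the new oxygen status will be selected". Nothing is said about death, discharge or a missing status. The source is the oxygen-status listing (16.2.6.4).

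The same section treats the WHO scale differently. "If patient dies before or on the time point", the status becomes 10; otherwise the last value is carried forward. Tables 14.2.3.1 and 14.2.3.5 then divide by N.

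Appendix 4, footnote 3, schedules vital signs with SpO2 and FiO2 on Days 1 to 3, then "further once daily while the patient is hospitalised, and on Days 8, and 31 (±3 days"). Day 15 is not among these days, although WHO clinical status is collected on it.

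**The concern.** A patient who died before the day has no oxygen status on it. As no rule says otherwise, that patient is not in n1. The rates and the Day 8 odds ratio then describe patients who are alive and have a record, and survival is itself an outcome that treatment may change (Section 3.5 lists mortality as an endpoint). If the sickest patients in one arm die, that arm's rate of oxygen or ventilator use among the remainder can fall. The comparison loses the protection of randomisation at the one time point where these rates are tested.

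The plan is also inconsistent with itself. Clinical status sets death to the worst category. Time to intensification counts death from any cause as an event. The undetectable viral load table divides by N and groups missing with detectable.

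**Working it through.** The documents give no rates, values of n1 or death counts for these tables, so there is no stated figure to reproduce. What follows is illustration. The only sourced input is N = 203 per arm (SAP Section 2.3). All counts of deaths, patients on oxygen and discharges are assumptions. Section 8 says recruitment stopped early, so the actual arms are smaller.

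Let O be patients alive and on oxygen that day, D deaths by that day, and M others with no record.

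- Plan: O / (N − D − M)
- All patients, death unfavourable: (O + D) / N

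**Deaths only (M = 0), plitidepsin v control**

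| O | D | Plan (n1) | All patients (N) |
|---|---|---|---|
| 20 v 20 | 4 v 4 | 20/199 v 20/199 = 10.1% v 10.1% (0.0) | 24/203 v 24/203 = 11.8% v 11.8% (0.0) |
| 20 v 20 | 4 v 10 | 20/199 v 20/193 = 10.1% v 10.4% (−0.3) | 24/203 v 30/203 = 11.8% v 14.8% (−3.0) |
| 20 v 20 | 20 v 10 | 20/183 v 20/193 = 10.9% v 10.4% (+0.6) | 40/203 v 30/203 = 19.7% v 14.8% (+4.9) |
| 16 v 20 | 16 v 6 | 16/187 v 20/197 = 8.6% v 10.2% (−1.6) | 32/203 v 26/203 = 15.8% v 12.8% (+3.0) |

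Differences in brackets are percentage points. With equal deaths and equal oxygen use nothing changes. With deaths of 2% v 5% or 10% v 5%, the two methods differ by about 3 to 4 points. In the last row the sign reverses.

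**Who else can be missing, day by day**

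- Day 4: Section 2.2 keeps patients in hospital for at least 4 days.
- Days 8 and 31: patients discharged before Day 8 return to clinic, and vital signs are scheduled on both days.
- Day 15: the visit is remote or on site, no vital signs are scheduled, and the plan does not say whether an earlier status carries forward.

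For Day 15, take one arm with N = 203, D = 10 and O = 20:

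- every discharged patient has a status: 20/193 = 10.4%;
- 50% to 80% discharged, half of them without a status: 20/142 = 14.1% to 20/112 = 17.9%;
- 50% to 80% discharged, none with a status: 20/91 = 22.0% to 20/31 = 64.5%.

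The Day 15 rate can therefore depend heavily on a derivation that the plan does not state.

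**The case against.** The strongest reply is that better-defined analyses stand beside these tables. WHO status on all four days uses every FAS patient with death as 10, so categories 5 to 10 already give the share on oxygen or dead. Time to intensification counts death, and mortality is reported by day. The per-period tables divide by N, so a patient who is ventilated and then dies still counts. This stands, and it is the main reason the point is minor.

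It is not a full answer. Patients enter needing oxygen, so the per-period oxygen table will be near 100% in every arm. In the per-period ventilation tables, a patient who dies without being ventilated counts as not requiring it. Neither corrects the Day 8 odds ratio.

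A reader might infer that discharged patients are lost on all four days, so that faster discharge could never show as benefit. The schedule does not support this: only Day 15 is exposed, apart from missed visits, and Day 15 is not tested. Nor does the SAP establish that the Day 15 denominator is simply those still in hospital. Listing 16.2.6.4 records changes of status, and a last entry of no oxygen might be carried forward. The derivation is unspecified; it is not shown to be wrong.

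A reader might also extend the point to the duration of advanced oxygen support, where "Only patients who required an advanced oxygen support will be included in the summary of the total duration of advanced oxygen support". That summary is descriptive and untested, and the number and percentage of users are shown with it.

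**Conclusion.** The point holds for deaths in all four tables and bears on the tested Day 8 comparison. It rests on reading n1 as written: with no rule for death, an earlier death means no data that day. For discharge it holds only as an unstated derivation on Day 15.

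The size cannot be computed from the documents. Under the assumed unequal deaths the shift is about 3 to 4 points, with a change of sign possible; with equal deaths and equal oxygen use it is nil. Severity is minor: the rates are other secondary endpoints without multiplicity control, formal testing is on Day 8 only, and the N-based WHO-scale and per-period tables sit alongside.

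**What to change.** - **Tables 14.2.3.6.1 and 14.2.3.11.1.** Divide by all FAS patients (N). Count death on or before the day as unfavourable, and label the outcome as on support or dead. Fill other missing days from WHO status by the rule already in Section 7.6.2.3, with categories 5 to 9 as oxygen and 7 to 9 as invasive ventilation/ECMO. Use the same set and outcome in the Day 8 logistic regression.
- **Tables 14.2.3.9.1 and 14.2.3.10.1.** Divide by N, show the dead and the missing as separate rows at each day, and carry the last recorded oxygen status forward after discharge. WHO status cannot fill these gaps because category 6 merges NIV with high flow. Counting each death as requiring both modalities would be a choice of estimand, so the Day 8 models here should state how the dead enter.
- **Existing n1 rates.** Keep them as descriptive.
- **Addendum.** Apply the same rules where it repeats Tables 14.2.3.9.1, 14.2.3.10.1 and 14.2.3.11.1 for Site ES40 and for all other sites.

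The cost is a change to footnotes and derivations and a rerun; no new data are needed. The addendum dates database lock to 26 April 2023, so the revised tables should be labelled supplementary. The downside is that the first two rates become composites with death and no longer measure support alone.

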## Table 14.2.3.6.2 Patients who Require Oxygen Therapy per Period (Full Analysis Set)

Period Variable	Plitidepsin 2.5mg (N=XXX)	Plitidepsin 1.5mg (N=XXX)	Control Arm (N=XXX)
From Day 1 to Day 4			
Require Oxygen Therapy, n (%)	xx (xx.x)	xx (xx.x)	xx (xx.x)
95% CI for Require Oxygen Therapy (%) [a]	XX.X – XX.X	xx.x – xx.x	xx.x - xx.x
Non Require Oxygen Therapy, n (%)	xx (xx.x)	xx (xx.x)	xx (xx.x)
Difference of Oxygen Therapy Rate (%) [b]	XX.X	XX.X	
95% CI for Difference of Oxygen Therapy Rate (%) [c]	XX.X – XX.X	XX.X - XX.X	
From Day 1 to Day 8			
Require Oxygen Therapy, n (%)	xx (xx.x)	xx (xx.x)	xx (xx.x)
95% CI for Require Oxygen Therapy (%) [a]	XX.X - XX.X	XX.X - XX.X	XX.X - XX.X
Non Require Oxygen Therapy, n (%)	xx (xx.x)	xx (xx.x)	xx (xx.x)
Difference of Oxygen Therapy Rate (%) [b]	XX.X	XX.X	
95% CI for Difference of Oxygen Therapy Rate (%) [c]	xx.x - xx.x	XX.X - XX.X	
Adjusted Odds Ratio [d,e]	X.XXX	X.XXX	
95% CI for Adjusted Odds Ratio [d,e]	x.xxx - x.xxx	x.xxx - x.xxx	
2-sided p-value [d]	X.XXX	X.XXX	
From Day 1 to Day 15			
Require Oxygen Therapy, n (%)	xx (xx.x)	xx (xx.x)	xx (xx.x)
95% CI for Require Oxygen Therapy (%) [a]	XX.X - XX.X	XX.X - XX.X	XX.X - XX.X
Non Require Oxygen Therapy, n (%)	xx (xx.x)	xx (xx.x)	xx (xx.x)
Difference of Oxygen Therapy Rate (%) [b]	XX.X	XX.X	
95% CI for Difference of Oxygen Therapy Rate (%) [c]	xx.x - xx.x	xx.x - xx.x	

From Day 1 to Day 31			
Require Oxygen Therapy, n (%)	xx (xx.x)	xx (xx.x)	xx (xx.x)
95% CI for Require Oxygen Therapy (%) [a]	XX.X - XX.X	XX.X - XX.X	xx.x - xx.x
Non Require Oxygen Therapy, n (%)	xx (xx.x)	xx (xx.x)	xx (xx.x)
Difference of Oxygen Therapy Rate (%) [b]	XX.X	XX.X	
95% CI for Difference of Oxygen Therapy Rate (%) [c]	XX.X - XX.X	XX.X - XX.X	

N = number of patients in analysis set; n = number of patients in each category; % = percentages are calculated based on N as the denominator; CI = Confidence interval.

[a] Clopper-Pearson 95% confidence interval.

[b] Difference of Oxygen Therapy Rate = Oxygen Therapy Rate for the plitidepsin arm - Oxygen Therapy Rate for control arm.

[c] Exact 95% confidence interval.

[d] Adjusted Odds Ratio, 95% CI and 2-sided p-values based on a stratified logistic regression model with fixed effects of treatment group and randomisation stratification factors, ie, geographical region (Europe vs. Rest of the World), Charlson Comorbidity Index (0-1 vs. >1) and pre-baseline Barthel index (≥90 versus <90) as derived using the eCRF data as covariates. [e] Statistics calculated relative to Control Arm.

Reference: Listing 16.2.6.4

Programming notes (not part of the table):

